### 7.2 Medical history

Medical history will be coded using MedDRA® and will be presented in the by-participant data listings.

Summary tables will include the number of participants (%) experiencing an event and the number of events. Participants will be counted only once for each SOC and PT level (categorical descriptive analysis).

### 7.3 Disease History

Disease history will be presented for SD-CP, SD-UP, MAD-CP and MAD-UP participants in the by-participant data listings. Summary tables will include the number of participants (%) experiencing each disease including liver disease, end stage renal disease, pruritus, suicidal indentations and so on (categorical descriptive analysis).

### 7.4 Hemodialysis History

Hemodialysis history will be presented for SD-UP and MAD-UP participants in the by-participant data listings.

The following parameters will be summarized:

#### Continuous descriptive analysis:

- Years required for chronic hemodialysis
- Years using current hemodialysis procedure
- Times a week that the patient undergoes hemodialysis
- Hemodialysis undergone per week
- Hours taken for hemodialysis procedure
- The dialysate - Sodium/Na (meq/L)
- The dialysate - Potassium/K (meq/L)
- The dialysate - Calcium/Ca (meq/L)
- The dialysate - Magnesium/Mg (meq/L)
- The dialysate - Bicarbonate/HCO3 (meq/L)
- The dialysate - Chloride/Cl (meq/L)
- The dialysate - Acetate (meq/L)
- The dialysate - Glucose (mg/dL)
- Dry weight
- Dialysis adequacy measurement (Kt/V and/or URR)

#### Categorical descriptive analysis:

- Residual renal function
- Type of hemodialysis
- Procedure membrane
- Type of heparin

### 7.5 Itch History

Itch history will be presented for MAD-CP and MAD-UP participants only in the by-participant data listings.

The following parameters will be summarized:

#### Categorical descriptive analysis:

- Number of patients having significant or consistent itch prior to liver/kidney disease diagnosis
- Time when itch is worse
- Does itching interfere patient's sleep

- Areas of body which are itchy
- Any secondary lesions to scratching ?
- Is itch more prominent in different seasons ?
- Seasons in which itch are worse
- Circumstance that aggravate itching
- Has UV light been used for itching

#### **7.6 Drug Screening and other Screening laboratory**

Drug Screening and other Screening laboratory including Hepatitis B Surface Antigen (HBsAg), Hepatitis C Antibody (HCVAb), Human Immunodeficiency Virus (HIV-1/HIV-2), urine drug test, Cotinine test, alcohol test, coagulation (including INR, APTT, PT), pregnancy test, and follicle-stimulating hormone (FSH) results will be presented in the by-participant data listings and will be summarized descriptively as described in section 3.1 (categorical descriptive analysis and continuous descriptive analysis) under the Safety Population.

#### **7.7 Inclusion/Exclusion Criteria Exceptions and Eligibility Criteria**

The subject eligibility responses as well as the violation of specific inclusion/exclusion criteria will be summarized descriptively and also presented in the by-subject data listings.

**8. TREATMENT EXPOSURE**

All study drug administration information (study drug administered (Yes/No), reason not administered, number of capsules taken, and date and time of administration will be presented in the by-participant data listings under the Safety Population.

Treatment exposure in duration and the number of capsules will be summarized descriptively as described in section 3.1 under the Safety population.

- The Treatment Exposure (duration in days) is defined as:  
Date of Last Study Drug Administration - Date of First Study Drug Administration + 1.

**9. PRIOR AND CONCOMITANT MEDICATIONS**

Concomitant medications will be summarized by Anatomical Therapeutic Chemical (ATC) class Level 2 and PT as noted in section 3.1 (categorical descriptive analysis). Participant who used the same medication on multiple occasions will only be counted once in the specific category (PT). PTs will be sorted alphabetically. In addition to the summaries by the coded terms, the number of participants who used at least one concomitant medication during the study will be presented under the Safety Population.

Prior medications and Concomitant medications will be presented in the by-participant data listings under the Enrolled Population.

## 10. PHARMACOKINETICS

### 10.1 Plasma PK Analysis

All PK summary tables will be based on the PK Population for plasma concentration data. All analyses will be summarized as described in section 3.1 (PK - continuous descriptive analysis). All listings will be based on the PK Population.

The following pharmacokinetic parameters will, where possible, be determined from the plasma concentrations of EP547 (and its metabolites if applicable) by non-compartmental method using Phoenix WinNonlin software (Version 8.1 or higher):

**Plasma Pharmacokinetic Parameters at non-steady state on Day 1 following single dose administration for SAD (SD) and MAD segments:**

Parameter	Definition
$C_{max}$	Maximum concentration which is directly determined from the plasma concentration time profiles
$T_{max}$	Time to maximum concentration. If the same $C_{max}$ concentration occurs at different time points, $T_{max}$ is assigned to the first occurrence of $C_{max}$ .
$AUC_{0-t}$	Area under the drug concentration-time curve, from time zero to the last measurable concentration using the 'Linear Up and Log Down' method
$AUC_{0-24hr}$	Area under the drug concentration-time curve, from time zero (time of dosing) to 24 hours post-dose using the 'linear Up and Log Down' method
$AUC_{0-48hr}$	Area under the drug concentration-time curve, from time zero (time of dosing) to 48 hours post-dose using the 'linear Up and Log Down' method (only for SAD cohort)

AUC 0-inf	
Area under the drug concentration-time curve, from time zero to infinity (<math>\infty</math>) using the following formula
 $AUC_{0-\infty} = AUC_{0-t} + \frac{C'_t}{\lambda_z}$ 
Where, <math>C'_t</math> is the observed concentration at the time t (last time point with a measurable plasma concentration above the quantification limit) at which quantification was still possible, the calculation of <math>\lambda_z</math> or <math>k_{el}</math> is given below.

AUC %extrap	
The percentage of the AUC that has been extrapolated beyond the last observed data point, using the following formula
 $AUC_{\%extrap} = \left( \frac{AUC_{0-\infty} - AUC_{0-t}}{AUC_{0-\infty}} \right) * 100$
$\lambda_z$ or $k_{el}$	
The apparent terminal elimination rate constant, will be estimated from a regression of <math>\ln(C)</math> versus time over the terminal log-linear drug disposition portion of the concentration-time profiles.

$t_{1/2}$	
Apparent terminal half-life, using the following formula
 $T_{1/2} = \frac{\ln(2)}{\lambda_z}$
CL/F	
Apparent total plasma clearance, using the following formula
 $CL/F = \frac{D}{AUC_{0-\infty}}$ 
Where D = Administered dose; <math>AUC_{0-\infty} = AUC_{0-inf}</math>

$V_z/F$	
Apparent terminal volume of distribution, using the following formula
 $V_z/F = \frac{CL/F}{\lambda_z} \text{ Or } \frac{Dose}{\lambda_z \times AUC_{inf}}$
Corrected M/P ratio for $C_{max}$	
Corrected metabolite to parent ratio for <math>C_{max}</math> is calculated using the following formulae
 
(<math>C_{max}</math> metabolite/<math>C_{max}</math> parent) *(Molecular Weight of parent drug/Molecular Weight of metabolite)

Corrected M/P ratio for AUC 0-t	
Corrected metabolite to parent ratio for AUC0-t is calculated using the following formulae
 
(AUC0-t metabolite/ AUC0-t parent) *(Molecular Weight of parent drug/Molecular Weight of metabolite)

**Plasma Pharmacokinetic Parameters at steady state on pre-defined days following multiple dose administration for the MAD-HS and MAD-CP segments (Day 1 and Day 7) and for the MAD-UP segment (Day 1, Day 2, Day 6, and Day 7)**

Parameter	Definition
C max	Maximum steady state concentration time over the dosing interval
C trough	The pre-dose trough concentration observed at the last planned timepoint prior to next dosing
T max	Time to reach maximum concentration over the dosing interval. If the same C max concentration occurs at different time points, T max is assigned to the first occurrence of C max .
AUC 0-t	Area under the drug concentration-time curve, from time zero to the last measurable concentration using the 'Linear Up and Log Down' method
AUC 0-τ	Area under the plasma concentration-time curve over a dosing interval using the 'Linear Up and Log Down' method
AUC 0-24hr	Area under the drug concentration-time curve, from time zero (time of dosing) to 24 hours post-dose using the 'linear Up and Log Down' method
AUC 0-48hr	Area under the drug concentration-time curve, from time zero (time of dosing) to 48 hours post-dose using the 'linear Up and Log Down' method
λ z or k el	The apparent terminal elimination rate constant, will be estimated from a regression of ln(C) versus time over the terminal log-linear drug disposition portion of the concentration-time profiles.
t ½	Apparent terminal half-life, using the following formula $T_{1/2} = \frac{\ln(2)}{\lambda_z}$
CL/F ss	Apparent total plasma clearance, using the following formula $CL/F_{ss} = \text{Dose} / AUC_{0-\tau}$
V z /F ss	Apparent terminal volume of distribution, using the following formula $V_z/F_{ss} = (\text{Dose}) / (\lambda_z \cdot AUC_{0-\tau})$
R auc	Accumulation ratio based on AUC, calculated as AUC 0-τ at steady state divided by AUC 0-τ after a single day
R cmax	Accumulation ratio based on C max , calculated as C max at steady state divided by C max after a single day
Corrected M/P ratio for C max	Corrected metabolite to parent ratio for C max is calculated using the following formula

---

	$(C_{\max} \text{ metabolite}/C_{\max} \text{ parent}) * (\text{Molecular Weight of parent drug}/\text{Molecular Weight of metabolite})$
Corrected M/P ratio for $AUC_{0-t}$	
Corrected metabolite to parent ratio for <math>AUC_{0-t}</math> is calculated using the following formula
 $(AUC_{0-t} \text{ metabolite}/ AUC_{0-t} \text{ parent}) * (\text{Molecular Weight of parent drug}/\text{Molecular Weight of metabolite})$

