Corrected M/P ratio for AUC 0-t	Corrected metabolite to parent ratio for AUC 0-t is calculated using the following formula (AUC 0-t metabolite/ AUC 0-t parent) *(Molecular Weight of parent drug/Molecular Weight of metabolite)
--	---

If the pre-dose concentration following first dose administration is  $\leq 5\%$  of the  $C_{max}$  value, the participant's data will be included in both pharmacokinetic and statistical analysis without any adjustment. If the pre-dose value is  $> 5\%$  of  $C_{max}$ , the subject will be dropped from both pharmacokinetic and statistical analysis.

Additional pharmacokinetic parameters may be determined where appropriate.

Corrected metabolite to parent ratio will be calculated for  $C_{max}$  and AUC0-t for steady state and non-steady state dosing profiles of HS segments (SAD & MAD).

Pharmacokinetic analysis will be carried out using actual doses and blood sampling times, where possible. If actual times are missing, nominal times may be used with sponsor approval.

Plasma concentrations of EP547 (and its metabolites if applicable) will be used as supplied by the bioanalytical laboratory. The units of concentration and resulting PK parameters, with amount or concentration in the unit, will be presented as they are received from the bioanalytical laboratory.

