14.1.7c	Medical History – SD-CP/SD-UP	Safety		×
14.1.7d	Medical History – MAD-CP/MAD-UP	Safety		×
14.1.7e	Medical History – FE-HS	Safety		
14.1.8c	Disease History – SD-CP/SD-UP	Safety		×
14.1.8d	Disease History – MAD-CP/MAD-UP	Safety		×
14.1.9c	Hemodialysis History – SD-UP	Safety		×
14.1.9d	Hemodialysis History – MAD-UP	Safety		×
14.1.10d	Itch History – MAD-CP/MAD-UP	Safety		×
14.1.11a	Drug Screening and Other Screening Laboratory Results – SAD-HS	Safety	×	×
14.1.11b	Drug Screening and Other Screening Laboratory Results - MAD-HS	Safety	×	×
14.1.11c	Drug Screening and Other Screening Laboratory Results - SD-CP/SD-UP	Safety		×
14.1.11d	Drug Screening and Other Screening Laboratory Results - MAD-CP/MAD-UP	Safety		×
14.1.11e	Drug Screening and Other Screening Laboratory Results – FE-HS	Safety		
14.1.12a	Study Drug Administration – SAD-HS	Safety	×	×
14.1.12b	Study Drug Administration – MAD-HS	Safety	×	×
14.1.12c	Study Drug Administration – SD-CP/SD-UP	Safety		×
14.1.12d	Study Drug Administration – MAD-CP/MAD-UP	Safety		×

Table Number	Table Title	Population	Interim	Final
14.1.12e	Study Drug Administration – FE-HS	Safety		
14.2	Efficacy/PK/PD			
14.2.1a	Plasma EP547 & EP3583 Concentrations by Treatment and Time – SAD-HS	PK	×	×
14.2.1b	Plasma EP547 & EP3583 Concentrations by Treatment and Time – MAD-HS	PK	×	×
14.2.1c	Plasma EP547 & EP3583 Concentrations by Treatment and Time – SD-CP/SD-UP	PK		×
14.2.1d	Plasma EP547 & EP3583 Concentrations by Treatment and Time – MAD-CP/MAD-UP	PK		×
14.2.1e	Plasma EP547 Concentrations by Treatment and Time – FE-HS	PK		
14.2.2a	Plasma EP547 & EP3583 Pharmacokinetic Parameters by Treatment – SAD-HS	PK	×	×
14.2.2b	Plasma EP547 & EP3583 Pharmacokinetic Parameters by Treatment – MAD-HS	PK	×	×
14.2.2c	Plasma EP547 & EP3583 Pharmacokinetic Parameters by Treatment – SD-CP/SD-UP	PK		×
14.2.2d	Plasma EP547 & EP3583 Pharmacokinetic Parameters by Treatment – MAD-CP/MAD-UP	PK		×
14.2.2e	Plasma EP547 Pharmacokinetic Parameters by Treatment – FE-HS	PK		
14.2.3.1a	Urine EP547 and EP3583 Concentrations by Treatment and Time – SAD-HS	Urine PK	×	×
14.2.3.2a	Urine EP547 and EP3538 Pharmacokinetic Parameters by Treatment – SAD-HS	Urine PK	×	×
14.2.4a	Plasma EP547 Dose Proportionality – SAD-HS	PK	×	×
14.2.4b	Plasma EP547 Dose Proportionality – MAD-HS	PK	×	×
14.2.4e	Analysis of Food Effect – FE-HS	PK		
14.2.5b	Skin EP547 & EP3583 Concentration by Treatment and Time – MAD-HS	Skin PK	×	×

Table Number	Table Title	Population	Interim	Final

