**19. LISTINGS**

Listing Number	Listing Title	Population	Interim	Final
16.2.1	Subject Disposition			
16.2.1.1	Analysis Populations	Enrolled	X	X
16.2.1.1e	Analysis Populations – FE-HS	Enrolled		
16.2.1.2	Subject Disposition	Enrolled	X	X
16.2.1.2e	Subject Disposition – FE-HS	Enrolled		
16.2.1.3	Subject Visits	Enrolled	X	X
16.2.1.3e	Subject Visits – FE-HS	Enrolled		
16.2.1.4	Subject Admission	Enrolled	X	X
16.2.1.4e	Subject Admission – FE-HS	Enrolled		
16.2.1.5	Screen Failures	Screen Failures	X	X
16.2.2	Protocol Deviations			
16.2.2.1	Protocol Deviations	Enrolled	X	X
16.2.2.1e	Protocol Deviations – FE-HS	Enrolled		
16.2.4	Demographic and Other Baseline Data			
16.2.4.1	Demographics and Baseline Characteristics	Enrolled	X	X
16.2.4.1e	Demographics and Baseline Characteristics – FE-HS	Enrolled		
16.2.4.2	Medical History	Enrolled	X	X
16.2.4.2e	Medical History – FE-HS	Enrolled		
16.2.4.3	Disease History	Enrolled		X
16.2.4.4	Itch History	Enrolled		X
16.2.4.5	Hemodialysis History	Enrolled		X
16.2.4.6	Drug Screening and Other Screening Labs	Enrolled	X	X
16.2.4.6e	Drug Screening and Other Screening Labs – FE-HS	Enrolled		

Listing Number	Listing Title	Population	Interim	Final
16.2.4.7	Inclusion/ Exclusion Criteria	Enrolled	X	X
16.2.4.7e	Inclusion/ Exclusion Criteria – FE-HS	Enrolled		
16.2.5	Treatment Administration			
16.2.5.1	Subject Randomization	Enrolled	X	X
16.2.5.1e	Subject Randomization – FE-HS	Enrolled		
16.2.5.2	Study Drug Administration	Enrolled	X	X
16.2.5.2e	Study Drug Administration – FE-HS	Enrolled		
16.2.6	Efficacy/PK/PD			
16.2.6.1	Plasma EP547 & EP3583 Concentrations	Enrolled	X	X
16.2.6.1e	Plasma EP547 Concentrations – FE-HS	Enrolled		
16.2.6.2	Plasma EP547 & EP3583 PK Parameters	PK	X	X
16.2.6.2e	Plasma EP547 PK Parameters – FE-HS	PK		
16.2.6.3	Urine EP547 and EP3583 PK Concentration	Enrolled	X	X
16.2.6.4	Urine EP547 and EP3583 PK Parameters	Urine PK	X	X
16.2.6.5	PK Skin Biopsy	Enrolled	X	X
16.2.6.6	[REDACTED]	Enrolled	X	X
16.2.6.7	[REDACTED]	Enrolled		X
16.2.6.8	[REDACTED]	Enrolled		X
16.2.6.9	[REDACTED]	Enrolled		X
16.2.6.10	[REDACTED]	Enrolled		X
16.2.6.11	[REDACTED]	Enrolled		X
16.2.6.12	[REDACTED]	Enrolled		X
16.2.6.13	[REDACTED]	Enrolled		X
16.2.6.14	[REDACTED]	Enrolled		X

Listing Number	Listing Title	Population	Interim	Final
16.2.6.15	[REDACTED]	Enrolled		X
16.2.6.16	[REDACTED]	Enrolled	X	X
16.2.6.17	[REDACTED]	Enrolled		

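### As written, SAP 10.1 applies dose-based CL/F and Vz/F to the metabolite as well as to EP547, and contradicts itself on where the metabolite-to-parent ratio is reported

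*SAP*

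**What the plan says.** SAP 10.1 introduces its plasma parameter tables by saying that the parameters will, where possible, "be determined from the plasma concentrations of EP547 (and its metabolites if applicable) by non-compartmental method".

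- **Single-dose table** (SAD, SD and MAD segments, Day 1). The CL/F row is headed "Apparent total plasma clearance, using the following formula" and divides D by AUC to infinity, "Where D = Administered dose". Vz/F uses the same dose.
- **Steady-state table** (MAD-HS, MAD-CP and MAD-UP). CL/Fss is dose over AUC for the dosing interval. Vz/Fss divides the same dose by λz times that AUC.
- **Outputs.** SAP section 18 plans "Plasma EP547 & EP3583 Pharmacokinetic Parameters by Treatment" for each segment except food effect, including the patient tables "Plasma EP547 & EP3583 Pharmacokinetic Parameters by Treatment – SD-CP/SD-UP" and "Plasma EP547 & EP3583 Pharmacokinetic Parameters by Treatment – MAD-CP/MAD-UP". Section 19 plans the listing "Plasma EP547 & EP3583 PK Parameters". The documents do not define EP3583; that it is the metabolite is an inference from these titles.
- **M/P ratio.** Both tables above carry rows for the molecular-weight-corrected ratio for Cmax and AUC0-t. Text after the food-effect parameter table then says: "Corrected metabolite to parent ratio will be calculated for" Cmax and AUC0-t, and names only the healthy-subject SAD and MAD segments.
- **Protocol.** Section 15.5 says that parameters will be calculated for EP547 and, as applicable, metabolites, but introduces the list that contains CL/F and Vz/F as coming from the EP547 concentration data.

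**The concern.** Dose over AUC estimates apparent clearance only for the compound that was dosed. The amount of EP3583 entering the body is whatever fraction of EP547 is converted, and that is unknown here. Dividing the EP547 dose by the EP3583 AUC therefore mixes formation, elimination and molecular weight under a clearance label. The SAP corrects for molecular weight in the M/P ratio and in the urinary metabolite parameters (SAP 10.2), but not in these four plasma parameters.

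The label matters most in the cholestatic and uremic segments, where metabolism or elimination may differ from healthy subjects. Anyone comparing the patient tables with the healthy-subject tables could take a difference in formation for a difference in metabolite clearance. The conflicting scope of the M/P ratio also leaves the programmer without a clear instruction for the same patients.

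**Working it through.** The plan gives no figure to reproduce. The check is of the formula itself.

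**Inputs from the SAP:** CL/F = D/AUC0-inf, CL/Fss = Dose/AUC0-τ, with the administered dose in each; corrected M/P = (metabolite AUC / parent AUC) × (MWp/MWm).

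**Inputs assumed, because the documents give none:** D = 75 mg; F = 0.9; CLp = CLm = 2 L/h; molecular weight ratio MWm/MWp = 1.0 or 1.2; fm from 1 down to 0.05. The metabolite is taken to form only from absorbed parent.

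**Step 1, parent.** AUCp = F × D / CLp, so D/AUCp = CLp/F = 2/0.9 = 2.22 L/h. The formula works for EP547.

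**Step 2, metabolite.** The mass formed is fm × F × D × (MWm/MWp), so AUCm = fm × F × D × (MWm/MWp) / CLm. Hence D/AUCm = CLm × (MWp/MWm) / (F × fm). Relative to CLm/F this is 1 / (fm × MWm/MWp). Vz/F and the steady-state versions carry the same factor.

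**Step 3, numbers.** Multiples of the true CLm/F:

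| fm (assumed) | MWm/MWp = 1.0 | MWm/MWp = 1.2 | Corrected M/P for AUC |
|---|---|---|---|
| 1 | 1.0 | 0.83 | 1.0 |
| 0.5 | 2.0 | 1.67 | 0.5 |
| 0.2 | 5.0 | 4.17 | 0.2 |
| 0.1 | 10 | 8.33 | 0.1 |
| 0.05 | 20 | 16.7 | 0.05 |

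A one-compartment parent-to-metabolite model, integrated numerically, gave the same values. The label is right only if fm × MWm/MWp = 1.

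**Step 4, what a difference between groups would mean** (equal molecular weights).

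- Start: fm = 0.2, CLm = 2 gives 2/(0.9 × 0.2) = 11.1 L/h.
- Halve formation: fm = 0.1 gives 2/(0.9 × 0.1) = 22.2 L/h.
- Double elimination: CLm = 4 gives 4/(0.9 × 0.2) = 22.2 L/h.

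The two causes give the same result. The corrected M/P for AUC equals fm × CLp/CLm, and it falls from 0.2 to 0.1 in both cases.

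**Step 5, scope of M/P.** The single-dose table is headed to cover SD segments, hence SD-CP and SD-UP, and the steady-state table names MAD-CP and MAD-UP. Both contain the ratio. The later sentence confines it to healthy subjects. Both instructions cannot be followed.

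**The case against.** The strongest reply is that the SAP never expressly says that CL/F or Vz/F will be computed for EP3583. It allows for what is possible, applicable and appropriate. The list cannot apply row by row to each analyte, since the M/P ratio needs both. The protocol ties its list to EP547 concentrations, and SAP section 15 declares no change to the planned analysis. Table titles do not show which parameters appear for which analyte. The analysis is descriptive, and no comparison of metabolite clearance between patients and healthy subjects is planned.

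Much of this stands, and it limits the weight of the point. It does not remove it. The natural meaning of the applicability wording is whether a metabolite is measured, and the tables show that EP3583 is. What is possible is governed by SAP 10.1.1: at least three points, adjusted R² of at least 0.8 and extrapolation below 20%. Metabolite data can pass all three. Where the SAP wants EP547 alone it says so, as in the dose-proportionality tables and the food-effect PK tables. It does not say so here.

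Two stronger readings are tempting. A reader might infer that the M/P ratio is omitted in the liver and kidney patients. The documents do not support that, because the parameter tables list it for those segments; the fault is a contradiction. Even if the restrictive sentence governs, EP547 and EP3583 Cmax and AUC0-t in patients are still tabulated and listed, so the ratio can be derived later. A reader might also infer that M/P would reveal a change in formation. Step 4 shows that it does not separate formation from elimination.

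**Conclusion.** The point holds as a minor defect of specification. Followed literally, SAP 10.1 yields for EP3583 a quantity labelled apparent clearance that equals CLm × (MWp/MWm) / (F × fm), and a volume carrying the same factor. The 2-, 5- and 10-fold multiples rest on assumed fm of 0.5, 0.2 and 0.1 and equal molecular weights; the true size cannot be known from the documents. If EP3583 also forms before EP547 reaches the circulation, F × fm is no longer the right denominator, but the amount formed is still unknown and the label still wrong.

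The scope of the M/P ratio is a separate inconsistency that needs resolving.

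Only secondary descriptive PK outputs are touched. The primary safety analysis, EP547 dose proportionality and the food-effect analysis are unaffected, and no data are lost.

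**What to change.** 1. In SAP 10.1, state that CL/F, Vz/F, CL/Fss and Vz/Fss are calculated for EP547 only, which matches the protocol's list. Cmax, Tmax, AUCs, half-life and accumulation ratios can remain for EP3583. Alternatively, keep the four for EP3583 but relabel them CLm/(F × fm) and Vm/(F × fm), with the dose in molar terms.
2. Align the sentence on the M/P ratio with the parameter tables, so that the ratio is reported in SD-CP, SD-UP, MAD-CP and MAD-UP. Describe it as an exposure ratio that does not by itself separate formation from elimination. In the same edit, settle the M/P rows in the food-effect list, since the PK tables for that segment name EP547 only.

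The cost is SAP wording and table shells. No new samples or data are needed.

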5.3. EP547

EP547 is a potent inverse agonist (low nM inhibitor) of MRGPRX4. In vitro studies have shown that EP547 antagonizes at least 18 MRGPRX4 agonists in several cell lines (overexpressing Chinese hamster ovary [CHO] and human embryonic kidney [HEK]-293 cells and in endogenously expressing SH-4 melanoma cells), utilizing an array of assay readouts (calcium mobilization, inositol phosphate-1 [IP-1] accumulation, and β -arrestin recruitment). In vivo absorption, distribution, metabolism, and excretion studies demonstrated that EP547 is highly bound to human plasma proteins, has high bioavailability with total volume of distribution similar to body water (approximately 0.8 L/kg), and biodistributes to sites of action in the skin and dorsal root ganglion. Pharmacokinetic (PK) studies in monkeys demonstrated that maximum (peak) plasma concentration (C_{max}) occurred approximately 2 hours after oral dosing with a half-life of approximately 18 hours. In vitro safety studies to date demonstrate no meaningful safety signals.

[REDACTED]

[REDACTED] Additional information for these studies is provided in the Investigator's Brochure.

In view of the available nonclinical data, further development of EP547 for the treatment of cholestatic or uremic pruritus is warranted. This first-in-human study is designed to assess the safety, tolerability, PK, and pharmacodynamics (PD) of single and multiple ascending doses of EP547 in healthy subjects and subjects with cholestatic or uremic pruritus. The outcome of EP-547-101 will inform the design of future clinical studies evaluating EP547.

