12.1. Blood Sampling for Pharmacokinetics

Blood sampling for PK of EP547 will be collected as follows:

- **SAD-HS, SD-CP, and SD-UP:** predose and at 0.25, 0.5, 1, 1.5, 2, 2.5, 3, 4, 6, 9, and 12 hours postdose on Day 1; 18, 24, and 36 hours postdose on Day 2; 48 hours postdose on Day 3; and at follow-up on Day 8.
- **MAD-HS:** predose and at 0.25, 0.5, 1, 1.5, 2, 2.5, 3, 4, 6, 9, 12, and 18 hours postdose relative to the dose of study drug on Day 1; predose on Day 2 through Day 6; predose and at 0.25, 0.5, 1, 1.5, 2, 2.5, 3, 4, 6, 9, 12, and 24 hours postdose relative to the last dose of study drug on Day 7; and at follow-up on Day 14 and Day 21.
- **MAD-CP:** predose and at 0.25, 0.5, 1, 1.5, 2, 2.5, 3, 4, 6, 9, 12, and 18 hours postdose relative to the dose of study drug on Day 1; predose on Day 2; predose on Day 4; predose and at 0.25, 0.5, 1, 1.5, 2, 2.5, 3, 4, 6, 9, 12, and 24 hours postdose relative to the last dose of study drug on Day 7; and at follow-up on Day 14 and Day 21.
- **MAD-UP:** predose and at 0.25, 0.5, 1, 1.5, 2, 2.5, 3, 4, 6, 9, 12, and 18 hours postdose relative to the dose of study drug on Days 1, 2, and 6; predose on Day 4; predose and at 0.25, 0.5, 1, 1.5, 2, 2.5, 3, 4, 6, 9, 12, and 24 hours postdose relative to the last dose of study drug on Day 7; and at follow-up on Day 14 and Day 21.

The MAD dosing and PK blood sampling schedule is summarized in [Appendix C](#). The assessment window for blood sample collection timepoints for the single and multiple dose segments is also included in [Appendix C](#).

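### SAP 10.1 assigns the steady-state clearance and volume formulas to MAD Day 1 and MAD-UP Day 2, before steady state; separately, it lists an AUC0-48hr that MAD sampling cannot support

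*SAP*

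**What the plan says.** Two parameter tables in SAP 10.1 cover the MAD segments.

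- The first is headed "Plasma Pharmacokinetic Parameters at non-steady state on Day 1 following single dose administration for SAD (SD) and MAD segments". It gives CL/F as dose over AUC0-inf, takes Vz/F from that, and restricts AUC0-48hr to the SAD cohort.
- The second is headed "Plasma Pharmacokinetic Parameters at steady state on pre-defined days following multiple dose administration for the MAD-HS and MAD-CP segments (Day 1 and Day 7"), and continues "for the MAD-UP segment (Day 1, Day 2, Day 6, and Day 7"). It gives CL/Fss = Dose/AUC0-τ and Vz/Fss = Dose/(λz × AUC0-τ), with no restriction by day. It also holds the accumulation ratios Rauc and Rcmax. It lists AUC0-48hr without the SAD restriction, and it lists neither AUC0-inf nor AUC%extrap.

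SAP 10.1.1.2 sets the regression-based parameters, naming CL/Fss and Vz/Fss among them, to NC (not calculable) unless adjusted R² is at least 0.8 and AUC%extrap is below 20%.

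The only half-life in the documents is in Protocol 5.3, for monkeys: "with a half-life of approximately 18 hours". For all three MAD segments, Protocol 12.1 ends blood sampling with "and 24 hours postdose relative to the last dose of study drug on Day 7; and at follow-up on Day 14 and Day 21". CL/F and Vz/F are secondary PK parameters for the MAD segments (Protocol 15.2.2, SAP 2.3.2).

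**The concern.** Dose over AUC0-τ equals apparent clearance only when the AUC over one dosing interval equals the single-dose AUC0-inf, which is what steady state means for linear kinetics. Day 1 follows the first dose, so it cannot qualify, and the SAP's own first table calls MAD Day 1 non-steady state. Before accumulation is complete AUC0-τ is too small, so CL/Fss and Vz/Fss are too large.

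At stake is the reading of a secondary PK parameter. A fall in CL/Fss from early to late days would look like time-dependent clearance when it is only accumulation. In MAD-UP, Day 1 is a dialysis day and Day 2 is not. If early values were reported without the 20% limit, CL/Fss would fall by a factor of 1.68/1.19 = 1.41 at an 18 h half-life with no dialytic clearance at all.

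The AUC0-48hr entry is a separate problem: a parameter is promised that the MAD schedule cannot deliver.

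**Working it through.** The documents give no figure for this point, so there is none to reproduce.

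**Inputs.** τ = 24 h, once daily for 7 days (Protocol 7.1.1 to 7.1.3). Half-life about 18 h and tmax about 2 h, both from monkeys (Protocol 5.3). No human half-life is given, so it is varied from 6 to 36 h as an assumption.

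**Model.** Linear one-compartment kinetics, constant clearance, no dialysis removal. Let x = exp(−ln2 × 24 / t½). On dosing day n, AUC0-τ / AUC0-inf = 1 − xⁿ, so Dose/AUC0-τ overstates CL/F by 1/(1 − xⁿ) − 1. Vz/Fss carries the same factor, since λz is common to both.

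At 18 h, x = 2^(−24/18) = 0.397. Day 1: 1/0.603 − 1 = 66%. Day 2: 1/(1 − 0.397²) − 1 = 19%.

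Where a range is shown, the first figure is this formula and the second adds first-order absorption with tmax 2 h.

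| Half-life | Day 1 | Day 2 | Day 6 | Day 7 |
|---|---|---|---|---|
| 6 h (assumed) | 6.7–7.3% | 0.4% | 0.0% | 0.0% |
| 12 h (assumed) | 33–35% | 6.7–6.9% | 0.0% | 0.0% |
| 18 h (monkey) | 66–68% | 19% | 0.4% | 0.2% |
| 24 h (assumed) | 100–103% | 33–34% | 1.6% | 0.8% |
| 36 h (assumed) | 170–174% | 66–67% | 6.7% | 4.1% |

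**Effect of the 20% limit.** In the simple model, AUC%extrap from the 24 h point equals x on every day: about 40% at 18 h and 63% at 36 h. A value passes only if x < 0.20, that is t½ < 24 × ln2/ln5 = 10.3 h (10.1 h with absorption). Among values that pass:

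- Day 1: at most 1/0.80 − 1 = 25%.
- Day 2: at most 1/(1 − 0.20²) − 1 = 1/0.96 − 1 = 4.2%.

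In MAD-UP the last sample after the Day 2 dose is at 18 h, because the Day 3 predose draw is for MAD-HS only (Protocol Appendix C). Day 2 AUC0-τ must therefore itself be extended to 24 h. A tail taken from 18 h is larger, so the limit bites sooner and 4% remains an upper bound.

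**AUC0-48hr in MAD.** After the doses on Days 1, 2 and 6, the next dose is given at 24 h, so a 48 h area would include a second dose. After Day 7, the sample following 24 h is on Day 14, a gap of 6 days, so a 48 h area would rest on interpolation across that gap or on extrapolation.

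**The case against.** The strongest reply is that SAP 10.1.1.2 names CL/Fss and Vz/Fss and suppresses them when 20% or more of the AUC is extrapolated; SAP 10.4.1 repeats the 20% criterion as a general setting. On that reading the large figures in the table never reach a report. This stands, with two limits. The steady-state table does not list AUC%extrap, so it is unclear how the criterion applies there. And it tests the size of the tail, not whether steady state has been reached: on 24 h data it would give about 40% on Day 7 as well at an 18 h half-life, removing valid values with the invalid ones.

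Second, MAD Day 1 already has the right formula. True, but that leaves two conflicting definitions for one day and does nothing for MAD-UP Day 2.

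Third, the early days have to be in the table because Rauc and Rcmax need AUC0-τ and Cmax after the first dose. Also true, and a reason to keep those two parameters, not CL/Fss and Vz/Fss.

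Fourth, no planned analysis uses early-day CL/Fss. PK is descriptive, dose proportionality uses Cmax, Ctrough and AUCs, and accumulation is reported directly through the ratios. This limits the harm to misread summary tables.

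**Conclusion.** The point holds as an error in definition with a bounded effect. The formulas are assigned to days on which they overstate clearance and volume: by at most about 25% (Day 1) and 4% (Day 2) if the 20% limit is applied to the 24 h profile. Otherwise the size depends on half-life, as tabulated: 66–68% and 19% at 18 h. Days 6 and 7 are close to unbiased, under 1% at 18 h and 4–7% at 36 h. These figures assume linear kinetics and ignore dialysis; the direction before steady state does not depend on the half-life chosen.

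A reader might infer more than the documents support:

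- That MAD clearance in general is overstated. Only Day 1 and, in MAD-UP, Day 2 are affected.
- That reported clearance will be wrong by a factor of 1.7 or 2.7. Those factors need an 18 h monkey or an assumed 36 h half-life, and also need the 20% limit not to be applied.
- That the bias hides impaired elimination in patients. With the limit applied, a longer half-life makes NC more likely, not an inflated value.
- That AUC0-48hr contributes to the overstatement. It enters neither formula. Its only stated use is renal clearance in SAD-HS (SAP 10.2), and its listing for MAD is a separate error.

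**What to change.** In SAP 10.1:

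- Limit CL/Fss and Vz/Fss to Day 7, and to Days 6 and 7 in MAD-UP.
- On MAD Day 1, use only the existing CL/F = Dose/AUC0-inf. Keep Day 1 AUC0-τ and Cmax for Rauc and Rcmax.
- On MAD-UP Day 2, report no clearance or volume.
- Delete AUC0-48hr from the MAD table.

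It would also help to state in 10.1.1.2 whether, and on which profile, the 20% limit applies to CL/Fss and Vz/Fss.

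The cost is SAP wording only, with no new samples or data. A few early-day cells are no longer reported.
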